9.10 Subject Monitoring

Beginning with informed consent, subjects will be monitored throughout the study by the clinical sites' staff for adverse events.

In Part 1 of the study (SAD), an Investigator will be on site/campus for drug administration and until 4 hours after administration and available on call for the remainder of the dosing period. In Part 2 of the study (MAD), an Investigator will be on site for each morning drug administration and until 4 hours after morning administration on Days 1, 4, 7, 10, and 13. An Investigator will also be on call for the remainder of the study. If necessary, a physician, either at the clinical site/campus or in a nearby hospital will administer treatment for any adverse event(s). A crash cart or emergency bag containing the necessary rescue material and appropriate medications will be available in the clinic to allow rapid intervention in case of emergency.

Safety parameters, including laboratory results, vital signs, pulse oximetry, and ECG, will be assessed by the Investigator or delegate, using the clinical site's criteria for biomedical laboratory and ECG acceptance ranges as suggested guidelines in making the medical assessment.

Scheduled safety measurements will be repeated according to appropriate clinical site SOPs or upon request from a physician. Any abnormal repeated measurement will be evaluated by a physician and repeated if judged necessary. Further action may be taken upon physician's request.

Unless otherwise specified or for subject safety, when the timing of some assessments coincide with other assessments or procedures, the following priority order and sequence should be adhered to, whenever possible: ECG, vital signs, pulse oximetry, blood samples for PK, clinical laboratory samples, and physical examination.

Subjects will be advised to notify their health care professional(s) (eg, physician, dentist, and/or pharmacist) that they are participating in a clinical research study on an experimental drug called nalbuphine (NAL ER) before taking any medicines or undergoing any medical procedure.

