4.2 Schedule of Events – Part 2 (Multiple Ascending Dose)

Procedure	Screening (Day -28 to Day -2)	Cohort 6												Dis-charge D16	Study Exit D17	Early Termination ⁱ
		D-1	D1	D2 D3	D4	D5 D6	D7	D8 D9	D10	D11 D12	D13	D14 D15				
Informed consent	X															
Review inclusion/ exclusion	X	X	X													
Demographic data	X															
Medical and medication histories	X															
Review and monitoring of AEs and concomitant medications	X	X	X	X	X	X	X	X	X	X	X	X	X	X	X	X
Physical examination ^a	X	X												X		X
Height, weight, and BMI	X															
Vital signs ^b	X	X	X	X	X	X	X	X	X	X	X	X	X	X		X
Body temperature	X	X												X		X
12-lead ECG ^c	X	X	X	X	X	X	X	X	X	X	X	X	X	X		X
Pulse oximetry ^d	X	X	X	X	X	X	X	X	X	X	X	X	X	X		X
Clinical chemistry ^e	X	X				X			X					X		X
Hematology ^e	X	X				X			X					X		X
Coagulation (PT, aPTT, and INR) ^e	X	X												X		X
HIV and hepatitis	X															
Urinalysis ^e	X	X												X		X
WI-NRS ^f	X	X	X	X	X	X	X	X	X	X	X	X	X	X		X
Urine alcohol and drug screen	X	X														
Urine and serum pregnancy test (as applicable)	X	X												X		X
Confinement ^g		X	X	X	X	X	X	X	X	X	X	X				
Drug administration 27 mg qd			X													
Drug administration 27mg bid				X												
Drug administration 27 mg (morning) and 54 mg (evening)					X											
Drug administration 54 mg bid						X										

Procedure	Screening (Day -28 to Day -2)	Cohort 6												Dis-charge D16	Study Exit D17	Early Termination ⁱ
		D-1	D1	D2 D3	D4	D5 D6	D7	D8 D9	D10	D11 D12	D13	D14 D15				
Drug administration 54 mg (morning) and 108 mg (evening)							X									
Drug administration 108 mg bid								X								
Drug administration 108 mg (morning) and 162 mg (evening)									X							
Drug administration 162 mg bid										X						
Drug administration 162 mg qd											X					
PK samples ^h			X	X	X	X	X	X	X	X	X	X	X	X	X	X

- A complete physical examination will be performed at screening. A brief physical examination will be performed on Day -1 and Day 16. The complete physical examination will include at least the following components: head, eyes, ears, nose, throat (HEENT), neck, lungs, abdomen, skin, cardiovascular and musculoskeletal evaluation, and general neurological examination.

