Based on the overall safety and tolerability observed in the subjects with mild and moderate impairment, at the completion of all doses tested, it will be determined by the Safety Committee whether or not it is safe to proceed with dosing for the first 2 subjects with severe Impairment. After review of the safety and tolerability for the first 2 severe subjects dosed at 27 mg, it will be determined whether or not to complete that dose level for the remaining severe subjects.

At the completion of all subjects dosed in the cohort, there will be an evaluation of safety and tolerability to determine whether to proceed to the next dose level for this group.

The Safety Committee will be composed of at least the Investigators and one medically qualified Sponsor representative. Some adjustments to the currently outlined doses and/or dosing regimen may be implemented by the Safety Committee, but the dose to be administered in a given dose cohort will not exceed the one currently outlined in the protocol.

Drug administration in Part 2 of the study (MAD) may be initiated following satisfactory review of the safety and tolerability data from Groups 1 and 2 (mild and moderate impairment) from Part 1 of the study (SAD) by the Safety Committee. Depending on safety and tolerability as well as on available PK data, the dose escalation scheme may be modified such that intermediate dose levels are administered. The dosage regimen (once daily versus twice daily) will be confirmed following review of PK data from Part 1 of the study (SAD).

If in the judgement of the Safety Committee the Part 1 PK data demonstrates dose linearity across the dose range in both the mild and moderate hepatic impairment subjects (Group 1 and Group 2 subjects), such that PK modeling can be predictive of steady state dosing levels, a decision may be made to end the study without conducting Part 2 of the study

In Part 2 of the study (MAD), subjects will receive a single 27 mg dose in the morning of Day 1. Starting on Day 2, doses will be subsequently escalated for each subject to twice daily, 12 hours apart, 27 mg, 54 mg, 108 mg, and 162 mg over 13 days. On the last treatment day, (Day 13), subjects will receive a single 162 mg dose in the morning. Subjects will remain at each dose level for 2-3 days (minimum 5 consecutive doses) with dose escalation predicated on tolerability of the prior dose (See Section [9.14.4](#) for dose escalation stopping rules).

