9.10.1 Vital Signs

Blood pressure, heart rate, and respiratory rate will be measured in a sitting position after at least 5 minutes of sitting (except for safety reasons).

In Part 1 of the study (SAD), blood pressure, heart rate, and respiratory rate will be measured at screening, in the morning on Day -1, pre-dose, approximately 1, 2, 4, 6, 8, 12, 24, and 48 hours post-dose, and on Day 4. Body temperature will be measured at screening, Day -1, and Day 4.

In Part 2 of the study (MAD), blood pressure, heart rate, and respiratory rate will be measured screening, in the morning on Day -1, pre-morning dose every day (Days 1 to 13), approximately 1, 2, 4, 6, 8, and 12 hours post-morning dose on Day 1 and Day 13, approximately 2 and 6 hours post-morning dose on Days 2 to 12, and once on Days 14, 15, and 16. Body temperature will be measured at screening, Day -1, and Day 16.

When vital signs measurements coincide with a blood draw, they should preferably be performed before the blood collection whenever possible. A time window of 15-20 minutes for vital signs will be allowed if there are multiple procedures at the same time point.

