9.10.2 Pulse Oximetry

Pulse oximetry will be performed at the screening visit. Baseline continuous pulse oximetry will be performed during the nighttime of Day -1 (minimum of 8 hours prior to first dose administration). Oxygen saturation will be monitored using a desaturation lower limit alarm of 92%. For subjects in Cohorts 1 to 4 and 6, if desaturation falls below the 92% lower limit alarm during the nighttime on Day -1, the Investigator has the discretion to lower their alarm limit on the pulse oximeter for subsequent nighttime monitoring in the study for that subject. In the event of desaturation below the lower limit alarm during the nighttime, the subject will be managed at the Investigator's discretion.

For Part 1 of the study (SAD), following the dose and throughout study conduct, oxygen saturation will be measured via pulse oximetry at pre-dose and 1.5, 4.5, and 8 hours post-dose. Oxygen saturation will be monitored via continuous pulse oximetry overnight beginning at bedtime and until awaking the next morning from Day 1 to end of confinement with oxygen saturation measurements specifically recorded at approximately midnight and 4 am.

For Part 2 of the study (MAD), following the first dose and throughout study conduct, oxygen saturation will be measured via pulse oximetry at pre-morning dose, at 1.5, 4.5, and 8 hours following the morning dose, and at 2 hours following the evening dose. Oxygen saturation will be monitored via continuous pulse oximetry beginning at bedtime and until awaking the next morning from Day 1 to end of confinement with oxygen saturation measurements specifically recorded at approximately midnight and 4 am.

Pulse oximetry measurements may be collected within 10 minutes before or after the specified time point.

9.10.3 12-lead ECG

For Part 1 of the study (SAD), a 12-lead ECG will be performed at screening, in the morning on Day -1, pre-dose, approximately 1, 2, 4, 6, 8, 12, 24, and 48 hours post-dose, and on Day 4.

For Part 2 of the study (MAD), a 12-lead ECG will be performed at screening, in the morning on Day -1, pre-morning dose every day (Days 1 to 13), approximately 1, 2, 4, 6, 8, and 12 hours post-morning dose on Day 1 and Day 13, and once on Days 14, 15, and 16.

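### In Part 2 no vital signs or ECG are planned for about 12 hours after the first dose of each new level, because increases are given in the evening and these readings follow the morning dose

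*Protocol*

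**What the plan says.** **Dosing.** Protocol 9.4 escalates Part 2 subjects "to twice daily, 12 hours apart, 27 mg, 54 mg, 108 mg, and 162 mg over 13 days", and "with dose escalation predicated on tolerability of the prior dose". In the titration table each increase falls on the evening dose of a split day: Day 4 (27 mg, then 54 mg), Day 7 (54, then 108) and Day 10 (108, then 162). The schedule in 4.2 agrees; its Day 4 row begins "Drug administration 27 mg (morning) and 54 mg (evening"). SAP Table 3-2 repeats the same doses.

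**Vital signs (9.10.1).** These are taken before each morning dose and "approximately 2 and 6 hours post-morning dose on Days 2 to 12". Days 1 and 13 have a fuller series, also after the morning dose.

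**ECG (9.10.3).** One tracing is taken before each morning dose. Post-dose series are planned only on Days 1 and 13.

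**Investigator presence (9.10).** The Investigator is on site for each morning dose and "until 4 hours after morning administration on Days 1, 4, 7, 10, and 13", and on call otherwise.

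**Oximetry (9.10.2).** This is the one measurement tied to the evening dose: it is read through the day "and at 2 hours following the evening dose", then continuously overnight, with values recorded around midnight and 4 am.

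**Stated rationale (5.2.4).** The protocol cites a label warning on respiratory depression. The label recommends monitoring respiration, particularly when nalbuphine is started or its dose is raised.

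**The concern.** Safety and tolerability are a primary objective (6.1), and each step up depends on how the previous dose was tolerated. One would therefore expect planned readings to follow the first dose of each new level. On Days 4, 7 and 10 the post-dose vital signs and the 4-hour on-site period follow the last dose of the outgoing level instead. Respiratory rate is one of the scheduled vital signs, and the protocol itself cites a recommendation to watch respiration when the dose is raised, yet no such reading is planned that evening or night.

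What is at stake is knowledge of blood pressure, heart rate, respiratory rate and ECG around the peak of a subject's first dose at 54, 108 and 162 mg. Subjects may enter Part 2 without having been in Part 1. For them this is their first exposure to the level.

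**Working it through.** There is no sample size or power figure to reproduce. The check puts the titration table and the monitoring times on one clock.

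Inputs: evening dose 12 hours after the morning dose (9.4); vital signs before the morning dose and at 2 and 6 hours (9.10.1); ECG before the morning dose (9.10.3); on-site window 0 to 4 hours on Days 4, 7 and 10 (9.10); oximetry 2 hours after the evening dose (9.10.2).

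Formula: hours from the first higher dose = hours after that day's morning dose − 12. The result is the same for all three split days.

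| Event | Hours after morning dose | Hours from first higher dose |
|---|---|---|
| Required on-site window | 0 to 4 | −12 to −8 |
| Last vital signs before the increase | 6 | −6 |
| First dose of the new level | 12 | 0 |
| Evening oximetry reading | 14 | +2 |
| Next vital signs and next ECG (before next morning dose) | about 24 | about +12 |
| Vital signs after the second dose of the level | 26 and 30 | +14 and +18 |

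Results:

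- Planned blood pressure, heart rate, respiratory rate or ECG readings between 0 and about 12 hours after the first higher dose: none, for 3 of 3 increases.
- The steps are 54/27 = 2, 108/54 = 2 and 162/108 = 1.5.
- The interval between consecutive sets of vital signs that spans each increase is about 24 − 6 = 18 hours.
- The required on-site window ends 12 − 4 = 8 hours before the increase.

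Does the peak fall in the gap? Table 2 in 5.1.1.2 (TR01, healthy subjects, multiple dosing) gives median Tmax of 3 hours at 54 mg bid, 5 at 108 mg bid and 4 at 162 mg bid. The individual ranges are 2 to 6, 3 to 9 and 2 to 6 hours. All of these values lie before 12 hours.

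What do later days supply? The table gives six doses at each level, which satisfies the requirement in 9.4 of at least five in a row. Vital signs 2 and 6 hours after dosing are planned for the new level on Days 5, 6 and 7 (54 mg), Days 8, 9 and 10 (108 mg) and Days 11 and 12 (162 mg); Day 13 has the full series. ECGs on Days 2 to 12 are pre-dose only, so in Part 2 the first post-dose series at a raised level is on Day 13, at 162 mg.

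**The case against.** The other side has a good deal to say, and most of it stands.

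- **The evening is monitored.** Oximetry is read at 2 hours and runs overnight with an alarm (9.10.2). An overnight fall of more than 10% from the subject's lowest baseline value, sustained for 5 minutes, counts as a DLT event (9.14). Staff watch confined subjects for adverse events, an Investigator is on call, and events after the evening dose are summarised under SAP 7.2. A reader might infer that first-exposure safety data are missing altogether. The documents do not support that.
- **Part 1 comes first.** Each level is given there as a single dose, with vital signs and ECG at 1, 2, 4, 6, 8, 12, 24 and 48 hours, and the Safety Committee reviews it before Part 2. The Part 2 evening dose is therefore not this population's first monitored exposure. It may still be an individual's first, and in Part 2 it is added to accumulated drug (factor 1.6 in TR01).
- **The second dose has vital signs the next morning.** With accumulation, exposure then should be at least as high. This limits the gap to the first dose, but does not fill it.
- **No mislabelling is shown.** A reader might infer that readings on Days 4, 7 and 10 will be reported as the new level. The SAP summarises by time point, and those time points precede the evening dose. The days are also intensive PK days for the outgoing level, which may explain the morning timing. That the on-site period was meant as cover for the increase is only an inference.
- **The sections do not contradict each other.** The dosing and monitoring texts are compatible as written. The mismatch is with the rationale in 5.2.4 and the tolerability condition in 9.4.
- **Part 2 may not be run** (9.14.5). The schedule should still be coherent if it is.

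The protocol also accepts that time points in the sleep period may be missed after an evening DLT (9.11.1). That concerns follow-up after an event, and does not supply planned readings after an increase.

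**Conclusion.** The point holds in a limited form. For all three increases in dose level, no blood pressure, heart rate, respiratory rate or ECG is planned for about 12 hours after a subject's first Part 2 dose at that level, and that interval contains the expected peak. No other section closes the gap.

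It is confined to vital signs and ECG at that first dose. It does not extend to oxygenation, adverse event capture or the later doses of a level.

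The conclusion assumes that the titration table is followed as written (the Safety Committee may modify it) and that Tmax in hepatic impairment is similar to that in healthy subjects, which the documents do not establish. The 12-hour gap itself does not depend on Tmax. The change is worth making because it bears on a primary objective and costs little.

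**What to change.** Reconcile the titration table in 9.4 with 9.10, 9.10.1 and 9.10.3, and with the schedule in 4.2, so that planned vital signs, including respiratory rate, also follow the first evening dose of each new level. They could be taken with the 2-hour post-evening oximetry already scheduled. Two hours is earlier than all three TR01 medians (3, 5 and 4 hours), so that reading should not be presented as capturing the peak. Any later time nearer the expected peak is for the sponsor to set, as are ECG timing and physician cover.

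In SAP 7.4, state that these readings are attributed to the new dose level.

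Cost: with one added time point, three sets of readings per subject who completes the titration. With up to 16 subjects in Part 2 (8.1) that is at most 16 × 3 = 48 sets, taken in confined subjects when staff are already reading oximetry, plus wording changes in the protocol and SAP. A later time point would add readings and might disturb sleep.

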9.10.1 Vital Signs

Blood pressure, heart rate, and respiratory rate will be measured in a sitting position after at least 5 minutes of sitting (except for safety reasons).

In Part 1 of the study (SAD), blood pressure, heart rate, and respiratory rate will be measured at screening, in the morning on Day -1, pre-dose, approximately 1, 2, 4, 6, 8, 12, 24, and 48 hours post-dose, and on Day 4. Body temperature will be measured at screening, Day -1, and Day 4.

In Part 2 of the study (MAD), blood pressure, heart rate, and respiratory rate will be measured screening, in the morning on Day -1, pre-morning dose every day (Days 1 to 13), approximately 1, 2, 4, 6, 8, and 12 hours post-morning dose on Day 1 and Day 13, approximately 2 and 6 hours post-morning dose on Days 2 to 12, and once on Days 14, 15, and 16. Body temperature will be measured at screening, Day -1, and Day 16.

When vital signs measurements coincide with a blood draw, they should preferably be performed before the blood collection whenever possible. A time window of 15-20 minutes for vital signs will be allowed if there are multiple procedures at the same time point.

9.10.2 Pulse Oximetry

Pulse oximetry will be performed at the screening visit. Baseline continuous pulse oximetry will be performed during the nighttime of Day -1 (minimum of 8 hours prior to first dose administration). Oxygen saturation will be monitored using a desaturation lower limit alarm of 92%. For subjects in Cohorts 1 to 4 and 6, if desaturation falls below the 92% lower limit alarm during the nighttime on Day -1, the Investigator has the discretion to lower their alarm limit on the pulse oximeter for subsequent nighttime monitoring in the study for that subject. In the event of desaturation below the lower limit alarm during the nighttime, the subject will be managed at the Investigator's discretion.

For Part 1 of the study (SAD), following the dose and throughout study conduct, oxygen saturation will be measured via pulse oximetry at pre-dose and 1.5, 4.5, and 8 hours post-dose. Oxygen saturation will be monitored via continuous pulse oximetry overnight beginning at bedtime and until awaking the next morning from Day 1 to end of confinement with oxygen saturation measurements specifically recorded at approximately midnight and 4 am.

For Part 2 of the study (MAD), following the first dose and throughout study conduct, oxygen saturation will be measured via pulse oximetry at pre-morning dose, at 1.5, 4.5, and 8 hours following the morning dose, and at 2 hours following the evening dose. Oxygen saturation will be monitored via continuous pulse oximetry beginning at bedtime and until awaking the next morning from Day 1 to end of confinement with oxygen saturation measurements specifically recorded at approximately midnight and 4 am.

Pulse oximetry measurements may be collected within 10 minutes before or after the specified time point.

9.10.3 12-lead ECG

For Part 1 of the study (SAD), a 12-lead ECG will be performed at screening, in the morning on Day -1, pre-dose, approximately 1, 2, 4, 6, 8, 12, 24, and 48 hours post-dose, and on Day 4.

For Part 2 of the study (MAD), a 12-lead ECG will be performed at screening, in the morning on Day -1, pre-morning dose every day (Days 1 to 13), approximately 1, 2, 4, 6, 8, and 12 hours post-morning dose on Day 1 and Day 13, and once on Days 14, 15, and 16.

ECG will be performed after a resting time of at least 5 minutes in supine position. When ECG coincides with a blood draw, it should preferably be performed before the blood collection whenever possible. A time window of 15-20 minutes for ECGs will be allowed if there are multiple procedures at the same time point.

9.10.4 Physical Examination

For Parts 1 and 2 of the study, a complete physical examination will be performed at screening. The complete physical examination includes at least the following components: HEENT (head, eyes, ears, nose, and throat), neck, and lungs, cardiovascular, abdomen, skin, musculoskeletal evaluation, and general neurological examination. Body measurements will be performed at screening and will include: body weight, height measurement, and BMI.

For Part 1, a brief physical examination will be performed on Day -1 and Day 4.

For Part 2, a brief physical examination will be performed on Day -1 and Day 16.

9.10.5 Drug and Alcohol Screen

For Parts 1 and 2 of the study, urine drug screen (amphetamines, methamphetamines, barbiturates, benzodiazepines, tetrahydrocannabinol, cocaine, opiates, PCP, MDMA, methadone) and a urine alcohol screen will be performed at screening and in the morning on Day -1.

9.10.6 Pregnancy Test

For Part 1 of the study, urine and serum pregnancy tests will be performed (females only) at screening, in the morning on Day -1, and on Day 4 or upon early termination. For Part 2 of the study, urine and serum pregnancy tests will be performed (females only) at screening, in the morning on Day -1, and on Day 16 or upon early termination.

Urine pregnancy test results will be confirmed by lab serum pregnancy test results. Pregnancy test results must be available and review documented prior to dispensation of IP (when applicable).

9.10.7 Laboratory Assessments

All scheduled clinical laboratory tests will be performed following a fasting period of at least 8 hours.

